III.2.a Colonization of germ-free mice with human gut bacteria from HF and LF older adults: Fecal samples from 6 HF (3 males, 3 females) and 6 LF (3 males, 3 females) older adults will be transferred into sex-matched (with the goal of minimizing sex-associated gut microbial variability^[6, 7]) C57BL/6J germ-free mice for a duration of 5 weeks at the Germ-Free and Gnotobiotic Microbiology Core at the Harvard Digestive Disease Center (HDDC; Boston, MA). The transmissible effect of host phenotype by gut microbiota has been previously reported by transferring human fecal bacteria into C57BL/6J germ-free mice^[36-38]. Furthermore, the homogenous genetic background provided by inbred C57BL/6J germ-free mice allows for a cleaner system to dissect signals from gut bacteria-host interactions, and improves experimental reproducibility, when compared with genetically heterogeneous GFM^[39]. One fecal sample from each human donor will be transferred into 5 separate germ-free mice (based on the range of germ-free mice used in human fecal transfer experiments^[36, 38]), resulting in 60 mice colonized with human gut microbiota. 5 germ-free mice will not be colonized with fecal bacteria from older adults (germ-free control group). All recipient mice will be fed *ad libitum* with a commercial, sterilized mouse chow^[38]. Food consumption will be measured daily to ensure that changes in lean mass or physical function do not result because of differences in food intake.

III.2.b Measurement and analysis of the change in lean mass and physical function in mice colonized with human gut bacteria: Lean mass and physical function in mice colonized with human gut bacteria will be measured on day 0 (prior to colonization), 9, 18, 27 and 35 days post-colonization at the HDDC. Lean mass will be measured with use of quantitative magnetic resonance imaging (EchoMRI-3in1 instrument, Houston, TX)^[38]. Muscle strength will be measured using a grip strength meter for mice (Technical and Scientific Equipment GmbH, Bad Homburg, Germany)^[40]. Each mouse will firmly grab the pulling bar of the grip strength meter with both forepaws and then pulled gently backwards until it releases its grip. The peak force of each trial is considered the grip strength. A 1-liter beaker filled with water will be used as a swimming pool to test endurance capacity^[41].

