A weight (10% of body weight) will be attached to the tail of a mouse, which is then placed in the water. The amount of time that the mouse is able to maintain complete buoyancy will be recorded. The EchoMRI, grip strength meter and beaker/weight will be sterilized prior to use to ensure that germ-free conditions at the HDDC are maintained. Because [name] has previously measured lean mass and physical function in mice^[42, 43], he will perform these measurements at the HDDC.

Differences for the change in lean mass and physical function will be calculated relative to initial values. Statistical significance for the change in lean mass and physical function will be compared in mice colonized with fecal bacteria from HF or LF human donors and for germ-free mice that were not colonized with human gut bacteria with use of two-way ANOVA^[38].

III.2.c Bacterial taxa identification and association with the change in lean mass and physical function in mice colonized with human gut bacteria: Fecal pellets will be obtained from 5 germ-free mice at baseline, which will not be colonized with human gut bacteria. Five weeks post-colonization with human gut bacteria, fecal pellets will be collected from 60 mice (30 each from the HF and LF donors) and from the 5 germ-free mice that did not receive human gut bacteria. 16S rRNA gene profiling on these 70 fecal pellets will be performed as described in **Section III.1.a**.

Associations between gut bacteria-containing principal components and individual bacterial taxa with the 35-day change in lean mass, mouse grip strength and endurance capacity will be identified as described in **Section III.1.b**. Supervised machine learning (random forest) will be used to predict whether a sample came from a mouse colonized with HF or LF donor microbiota^[44].

The gut bacterial profile that is associated with the change in lean mass and physical function in mice colonized with HF or LF human fecal bacteria is expected to be similar to the gut bacterial profile that is associated with differentiation of HF from LF older adults. CIA will be used to identify associations between circulating metabolites with gut bacteria that collectively differentiate mice colonized with HF or LF gut bacteria.

A. Subject Characteristics

1) Subject eligibility criteria:

a) Inclusion criteria:

- i) Willing and able to sign the IRB approved informed consent form
- ii) Male and Female: males, 70-85y; females, 70-80y

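### The two-way ANOVA for the mouse experiment names no factors and cannot hold donor group, sex and day together, so sex, balanced by design, may be left out of the HF v LF test

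*Protocol*

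**What the plan says.** The mouse sections of the protocol and SAP carry the same text.

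- **Design (III.2.a).** "Fecal samples from 6 HF (3 males, 3 females) and 6 LF (3 males, 3 females) older adults" supply the bacteria, which go into mice of the donor's sex "with the goal of minimizing sex-associated gut microbial variability". Each donor's sample "will be transferred into 5 separate germ-free mice", giving 30 HF and 30 LF mice. For the control arm, "5 germ-free mice will not be colonized with fecal bacteria from older adults (germ-free control group"; the sex of these five is not given.
- **Measurement (III.2.b).** Lean mass and physical function are "measured on day 0 (prior to colonization), 9, 18, 27 and 35 days post-colonization". The outcome is the change from each mouse's starting value.
- **Test (III.2.b).** HF mice and LF mice are compared with each other and with "germ-free mice that were not colonized with human gut bacteria with use of two-way ANOVA". The two factors are not named, and sex, day and donor are not mentioned as model terms.
- **Power (Statistical Power paragraph under Aim 2).** An effect size of 2.6 with 12 human subjects is said to give 99% power, so the power statement counts donors.

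**The concern.** Donor group, sex and day are three crossed factors, and a two-way ANOVA has room for two. With five measurement days, group by day is a natural reading, and sex is then absent.

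Balance on sex keeps HF v LF free of sex bias whether or not sex is modelled. The gain in precision comes only if sex is in the model; otherwise a male-female difference in change is counted as unexplained donor-to-donor variation. What is at stake is a missed HF v LF effect in the experiment that is meant to show causation.

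The germ-free comparison is more exposed. Five controls cannot be half male and half female, so an unadjusted contrast with the sex-balanced colonized groups can carry part of any sex difference.

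**Working it through.** **The plan's own figure.** Reading the ± values as SDs, pooled SD = √((5.0² + 2.0²)/2) = 3.81, and d = (10.0 − 0.1)/3.81 = 2.60. With 6 v 6 donors and α = 0.05, power is 99.5% (two-sided normal), 98.1% (two-sided t, 10 df) or 99.4% (one-sided t). The stated 99% reproduces.

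**Assumptions for the check.** The documents give neither a sex difference in change nor a donor correlation. I assume:

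- a sex gap g of 0.5, 1.0 or 1.5, in units of the within-sex SD of one mouse's change (mouse SD);
- a donor intraclass correlation (ICC) of 0.3, with 0.2 and 0.5 as a range;
- a single time point.

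**Error term at donor level.**

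- Variance of a donor mean over 5 mice = 0.3 + 0.7/5 = 0.44, so SD = 0.663.
- Sex gap in donor-mean SDs: D = g/0.663.
- With sex left out, the 12 donors add 12 × (D/2)² = 3D² to the error sum of squares. Over 10 df, the expected error mean square is 1 + 0.3D².
- With sex in the model, the mean square stays at 1, on 9 df.

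**Results.** Power with sex modelled is from the noncentral t (9 df). Without sex it is from 400,000 simulated two-sided t-tests per cell, with 3 males and 3 females per group. An effect of 1.25 mouse SD is 1.25/0.663 = 1.88 donor-mean SD.

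| Sex gap g | D | Error mean square | Power at d = 2.6, sex out | Power at 1.25 mouse SD, sex out | Type I error, sex out |
|---|---|---|---|---|---|
| 0.5 | 0.75 | 1.17 | 97.1% | 79.0% | 3.6% |
| 1.0 | 1.51 | 1.68 | 92.6% | 64.7% | 1.4% |
| 1.5 | 2.26 | 2.53 | 80.4% | 42.5% | 0.3% |
| any, sex modelled | – | 1.00 | 97.9% | 82.7% | 5.0% |

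If the sexes do not differ, leaving sex out gives 98.1% and 83.6%, so modelling it costs at most about one point.

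For g = 0.5, 1.0 and 1.5, other ICCs give these powers without sex:

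- ICC 0.2: 97%, 91%, 75% at d = 2.6 (98% with sex); 86%, 71%, 46% at 1.25 mouse SD (89% with sex).
- ICC 0.5: 97%, 94%, 87% at d = 2.6 (98% with sex); 67%, 54%, 37% at 1.25 mouse SD (70% with sex).

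**If the mouse is the unit.** III.2.b speaks of mice and has no donor term. A 30 v 30 test with mice taken as independent, at ICC 0.3, has a simulated type I error of about 18%, 14% and 10% for the three gaps with sex left out, and about 20% with sex added but donor still ignored.

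**Germ-free contrast.** With k of 5 controls of one sex against a half-and-half group, the unadjusted bias is |k/5 − 1/2| × gap: 0.1 of the gap for 3/2, 0.3 for 4/1 and 0.5 for 5/0.

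**The case against.** The strongest reply is that the factors are not named, so nothing shows that sex is the one left out. A reader might infer that sex variance does fall into the HF v LF error. The documents do not support that. Group by sex on the 35-day change, the endpoint that III.2.c uses for its association analysis, is also a two-way ANOVA. Sex is then modelled, and power at d = 2.6 is 97.5% on 8 df. The plan also cites a published study for the method, which may settle the factors but is not available here. This reply stands, and it makes the loss conditional. It does not close the gap: under group by sex, the repeated measurements have no stated analysis, and a single-sex control group would leave an empty cell.

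Four further limits also stand:

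- **Direction.** A reader might infer that the HF v LF test is conservative. That holds only if donor is the unit. With mice taken as independent, the error rate is too high at ICCs of 0.2 to 0.5 for all three gaps. At ICC 0.1 it falls below 5% only at the 1.5 SD gap.
- **Scale.** A constant male-female difference in level cancels from an absolute change. Only a sex difference in change counts.
- **Size.** At the plan's effect size the loss is small unless the sex gap is large. The 42% figure needs both an assumed smaller effect and the largest assumed gap.
- **Blocking.** It would be too strong to say that the balance on sex is wasted. Its stated aim concerns microbial variability, and it still protects HF v LF from sex bias.

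**Conclusion.** The point holds as a gap in the specification with a conditional cost. The named method cannot contain group, sex and day, and neither document says which is dropped or what the unit is.

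If sex is dropped and donor is the unit, HF v LF is unbiased but loses power: from about 98% to 97%, 93% or 80% at d = 2.6, and from 83% to 79%, 65% or 42% at 1.25 mouse SD. These figures rest on an assumed ICC of 0.3 and assumed sex gaps of 0.5, 1.0 and 1.5 mouse SD in change. The 2.6 comes from adiposity, not lean mass or strength, which is why a smaller effect is shown beside it; 1.25 is itself an assumption.

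If mice are treated as independent, donor clustering is the larger problem, and adding sex alone leaves the type I error near 20% at ICC 0.3. Sex and donor therefore have to enter the model together. The germ-free contrast is open to sex bias of 0.1 to 0.5 of the sex gap until the controls' sex is fixed and the contrast adjusted.

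**What to change.** In III.2.b of both documents, replace the two-way ANOVA with a repeated-measures mixed model of change: donor group, sex and day as fixed effects, and donor and mouse within donor as random effects. HF v LF is then tested within sex at donor level. Name the primary contrast, for example the 35-day change, with a group-by-day term if it is taken at a single day. Germ-free mice have no donor, so say that each is its own unit.

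In III.2.a, fix the sex split of the five controls in advance with both sexes included, for example 3/2, and state that every germ-free contrast is sex-adjusted.

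The cost is a few sentences and one degree of freedom (9 instead of 10 at donor level), or about one point of power if the sexes do not differ. A sixth control mouse would allow an even split but is not needed.

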Bacterial taxa that differentiate HF from LF older adults: Principal co-ordinate analysis (PCoA) of the phylogeny based Unifrac distance metric^[32], which are derived from OTUs^[33] will be used to determine if the overall gut microbial profile in HF is significantly different when compared with LF older adults. The analysis of similarities function in the statistical software package PRIMER 6 (PRIMER-E Ltd., Lutton, UK^[34]) will be used to determine between-group statistical significance ($p \leq 0.05$). To identify bacterial taxa and relative abundance that are significantly different in HF when compared with LF older adults, linear discriminant analysis effect size (LEFSE)^[35] will be used. LEFSE is an algorithm for high-dimensional biomarker discovery and explanation that identifies bacterial taxa that characterize the difference between two or more biological conditions.

Test the causative role of human gut bacteria on the maintenance of lean mass and physical function: Although identification of gut bacteria that are associated with lean mass and physical function is an important observation, transplanting intact uncultured human fecal microbiota into recipient germ-free mice permits the donors' communities to be replicated and the causative role of their microbiota on outcome measures to be

discerned. For example, transplantation of human gut microbiota from 4 female twins discordant for kwashiorkor (the condition caused by severe dietary protein deficiency) into germ-free mice resulted in 86-90% of species-level taxa and ~90% of the functions encoded by the donor's microbiome being found in recipient mice, thereby implicating the gut microbiota as a causal factor on kwashiorkor^[36].

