Transplantation of gut microbiota from a healthy human adult into germ-free mice resulted in all bacterial phyla, 92% of bacterial classes and 88% of genus-level taxa being detected in the feces of recipient germ-free mice^[37]. Human gut bacteria-containing mice fed a high-fat western diet gained significantly more adiposity during the two weeks following transplantation than mice that consumed a low-fat, plant polysaccharide-rich diet^[37], evidence that demonstrates a causative role for diet-induced increases in adiposity by human gut bacteria. Similarly, transplantation of human gut microbiota from 3 twins (2 female and 1 male) discordant for obesity into germ-free mice resulted in ~75% of family-level bacterial taxa and 99.7% of the functions encoded by the donor's microbiome being represented in recipient mice, thereby resulting in a greater increase in adiposity in mice colonized with fecal microbiota from obese, when compared with its lean co-twin^[38].

Collectively, these studies demonstrate that transfer of gut bacteria from humans into germ-free mice is highly efficient, functions encoded by the transferred microbiome are maintained, and phenotypes are transmissible. The objective of **AIM 2** is to test the causative role of human gut bacteria on the maintenance of lean mass and physical function by transferring fecal microbiota from HF and LF older adults into germ-free mice.

Statistical Power: Germ-free mice colonized with fecal bacteria from obese humans gained significantly more adiposity than germ-free mice colonized with fecal bacteria from their lean co-twin ($10.0\% \pm 5.0\%$ compared with $0.1\% \pm 2.0\%$), a result that was significant 15 days after colonization^[38]. Based on these data, the resulting effect size of 2.6 is sufficient to obtain 99% power at a type-I error probability of 0.05 with a sample size of 12 human subjects. Accordingly, with the goal of identifying a similar change in lean mass and physical function, I propose to transfer fecal bacteria from 12 older adults into germ-free mice.

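### The mouse random forest specifies no donor hold-out, so with 5 mice per donor its default accuracy can reflect donor recognition rather than an HF/LF difference

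*Protocol*

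**What the plan says.** The design is in section III.2.a of both documents. The donors are "Fecal samples from 6 HF (3 males, 3 females) and 6 LF (3 males, 3 females) older adults", and "One fecal sample from each human donor will be transferred into 5 separate germ-free mice", "resulting in 60 mice colonized with human gut microbiota". Section III.2.c then collects pellets five weeks after colonization, 30 from each donor group, and states: "Supervised machine learning (random forest) will be used to predict whether a sample came from a mouse colonized with HF or LF donor microbiota". A methods source on supervised classification of microbiota (reference 44) is cited for this step.

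Nothing more is said about the classifier. Neither document mentions a training and test split, cross-validation, out-of-bag scoring, grouping by donor, a permutation test or an accuracy threshold.

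Two other statements bear on the point. The rationale for the mouse work is that transplantation "permits the donors' communities to be replicated" and that "transfer of gut bacteria from humans into germ-free mice is highly efficient". The AIM 2 power paragraph counts donors, not mice: the assumed effect is "sufficient to obtain 99% power at a type-I error probability of 0.05 with a sample size of 12 human subjects".

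**The concern.** HF or LF is a property of the donor, so all five mice of a donor carry the same label. If a mouse is tested while its siblings are in the training data, the forest does not need to learn anything that separates HF from LF communities. It only has to recognise whose community the mouse carries. This is leakage between training and test data, and it grows worse as colonization works better.

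This problem is distinct from the error term of the two-way ANOVA on lean mass and function. A donor term there would not change how the forest is scored.

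At stake is the meaning of the reported accuracy. A high value would invite the reading that an HF or LF signature had been transmitted to the mice, and the taxa ranked as important could be fingerprints of individual donors. The plan expects the profile found in mice to resemble the one separating HF from LF humans, so such a ranking could mislead that comparison too.

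**Working it through.** **1. Counts.** 6 + 6 = 12 donors; 12 × 5 = 60 mice; 6 × 5 = 30 per class. These agree with the documents.

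**2. The plan's own power figure.** The inputs, from the AIM 2 power paragraph, are 10.0 (SD 5.0) against 0.1 (SD 2.0).

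- Pooled SD = √((5.0² + 2.0²)/2) = 3.808, so d = 9.9/3.808 = 2.60, as stated.
- With 6 donors per group and α = 0.05, power is 0.9945 (normal, two-sided), 0.981 (noncentral t, two-sided) or 0.994 (noncentral t, one-sided).

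The stated 99% with 12 donors is reproduced. It concerns the mouse phenotype, not the classifier. It matters here because it takes the donor as the unit.

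**3. How often siblings stay in training.** Each tree is grown on 60 draws with replacement from 60 mice. Given that a mouse is out of bag, the 60 draws fall on the other 59.

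- A given sibling is in the tree with probability 1 − (58/59)^60 = 0.64, so on average 4 × 0.64 = 2.6 of its 4 siblings are in training.
- All four are absent with probability (55/59)^60 = 0.015.

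About 98.5% of out-of-bag votes therefore come from trees that have seen the same donor.

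**4. Accuracy when no HF/LF difference exists.** Null simulations used 12 donors × 5 mice, labels fixed by donor and a random forest. Donor ICC (the share of taxon variance due to donor) and the number of taxa are not in the documents, so both are varied. The 50- and 200-taxon runs used log-normal relative abundances, 200 trees and 40 data sets per setting. The 100-taxon column gives the range over two separate simulations where both covered a setting. Entries are mean accuracy in %. OOB is out-of-bag, CV is 5-fold cross-validation by mouse, and held out means one HF and one LF donor, with all their mice, left out per fold.

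| Donor ICC | 50 taxa: OOB / CV / held out | 100 taxa: OOB | 200 taxa: OOB / CV / held out |
|---|---|---|---|
| 0 | 47 / 50 / 52 | – | 46 / 50 / 51 |
| 0.1 | 55 / 59 / 50 | 58 | 59 / 66 / 51 |
| 0.3 | 72 / 74 / 50 | 75–79 | 84 / 86 / 50 |
| 0.5 | 86 / 87 / 54 | 90–94 | 96 / 96 / 52 |
| 0.7 | 96 / 95 / 52 | – | 100 / 100 / 50 |
| 0.8 | – | 99 | – |
| 0.9 | 100 / 100 / 50 | – | 100 / 100 / 46 |

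With 100 taxa and donor pairs held out, accuracy was 48–51%. The inflation is absent at ICC 0, rises with ICC, and disappears when whole donors are held out, as the leakage explanation predicts.

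**5. What counts as evidence.** If the 60 mice were treated as independent, 37/60 correct (62%) would give a one-sided binomial p of 0.046. Every mouse-level score in the table from ICC 0.3 upward exceeds 62% with no signal present.

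With donors as the unit, the binomial SD of the number correct would be √(12 × 0.25) = 1.73. Training sets overlap between folds, so held-out predictions are correlated, and the simulated null SD is 2.0–2.35. The simulated null tails are about 0.13–0.16 for at least 9 of 12 and 0.05–0.07 for at least 10 of 12. A donor-level permutation test respects this correlation. Within sex there are C(6,3) × C(6,3) = 20 × 20 = 400 arrangements.

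**The case against.** The strongest reply is that the plan is silent, not wrong. A reader might infer that the investigators have decided to score by mouse with no donor held out. The documents do not support that: no scoring method is named, and the cited methods source, not available here, may address validation. This objection stands. The defect is a missing specification. Silence still permits the leaking scores, and those are what the standard procedure returns by default.

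A second reply is that the ICC is assumed. This also stands. A reader might infer that near-perfect accuracy is bound to appear, but it needs an ICC of roughly 0.5 or more with 200 taxa, or 0.7 or more with 50. At 0.1 to 0.3 the false accuracy is 55–86%. The colonization percentages in the rationale describe donor taxa or functions found in recipients, not shares of abundance variance. They suggest similar siblings but do not fix an ICC.

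A third reply is that AIM 2 rests on the lean mass and function comparison, and that the forest carries no hypothesis test, power claim or decision. That is correct, and it limits the severity. It does not make a leaked accuracy interpretable.

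**Conclusion.** The concern holds as an under-specification with a material consequence. As written, the plan allows an accuracy that can measure donor recognition. With no HF/LF signal and 100 taxa, out-of-bag accuracy is about 58% at ICC 0.1, 75–79% at 0.3, 90–94% at 0.5 and 99% at 0.8, against about 50% with whole donors held out. These figures assume independent simulated taxa and an ICC that the documents do not supply.

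Two stronger conclusions are not supported. One is that the causal aim as a whole fails: the phenotype comparison is a separate analysis. The other is that 10 of 12 donors correct would be significant on a binomial count. The binomial tails are 0.073 for at least 9 and 0.019 for at least 10, but they assume independent predictions and understate the simulated tails given above.

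Grade: should be fixed. It is a supporting mouse analysis, and the error can be avoided at the analysis stage.

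**What to change.** In section III.2.c of both documents, add text to this effect:

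> Predictive performance will be estimated with all five mice of a donor kept in the same fold; in each of six folds, one HF and one LF donor are left out, by a pairing rule fixed before analysis. Any feature selection is done inside the training folds. Accuracy is reported per donor (12 units), with the rule for combining a donor's five mice stated in advance. Its p-value comes from rerunning the whole procedure under permutation of HF/LF labels over donors within sex (400 arrangements). Out-of-bag or mouse-level accuracy is not used as evidence.

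Donor grouping is the essential part. Leaving out one donor of each group keeps the training classes balanced at five donors each. Same-sex pairing is optional and would itself need fixing: 3 HF and 3 LF donors per sex allow 3! = 6 pairings per sex, 6 × 6 = 36 in all. The pairing should be a rule that can be reapplied to permuted labels.

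The cost is a short paragraph and some code, with no extra mice, donors or samples. The downside is a lower and less precise accuracy, because it rests on 12 donors. A complete reversal of the labels gives the same split of donors, so the smallest attainable p-value is in effect 2/400 = 0.005.
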